5. SELECTION OF STUDY POPULATION

5.1. Study Population

5.1.1. Inclusion Criteria

Each subject must meet all of the following inclusion criteria to be enrolled in the study:

1. Subject must be 40-80 years of age at the time of signing the Informed Consent Form (ICF);
2. Subject has well documented IPF satisfying the ATS/ERS/JRS/ALAT diagnostic criteria (Raghu, Collard et al. 2011). In the absence of a surgical lung biopsy, HRCT must be “consistent with UIP” defined as meeting either criteria A, B, and C, or criteria A and C, or criteria B and C below:
 - A. Definite honeycomb lung destruction with basal and peripheral predominance.
 - B. Presence of reticular abnormality AND traction bronchiectasis consistent with fibrosis with basal and peripheral predominance.
 - C. Atypical features are absent, specifically nodules and consolidation. Ground glass opacity, if present, is less extensive than reticular opacity pattern.
3. If on pirfenidone or nintedanib, subject must have been on a stable dose of pirfenidone or nintedanib for at least 3 months prior to screening without increase in FVC% predicted on two consecutive PFTs, including screening PFTs. Subjects may not be on both pirfenidone and nintedanib.
4. If not currently receiving pirfenidone or nintedanib, subject must have been off pirfenidone or nintedanib for ≥ 4 weeks prior to screening
5. Subject has a FVC $\geq 50\%$ and $\leq 90\%$ of predicted.
6. Subject has an Hb corrected and/or Hb uncorrected DLCO $\geq 25\%$ and $\leq 90\%$ of predicted.
7. Minimum distance on 6MWT of 150 meters.
8. Subject has a forced expiratory volume in 1 second (FEV₁)/FVC ratio > 0.70 .

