4.1 Efficacy endpoints

4.1.1 Primary efficacy endpoint

The primary efficacy endpoint for the study is the mean change from baseline in FVC [% predicted] from Baseline to Week 28. Data for FVC [% predicted] will be provided by BioMedical Systems (BMS) and analysed without any transformation or derivation. The specification on how this variable is measured and computed are provided in the BMS specification document (PRM 151-202 Analysis Plan FINAL Version 1.0 02MAY16).

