- Changes in serum and cellular biomarkers and response according to baseline genetic characteristics: [REDACTED] analysis may be provided at a later stage than the rest of the analyses, some or all the corresponding data may not be available at the time of the database lock.

Pharmacokinetic endpoints: Pentraxin levels will be assayed at baseline, before each study dose infusion and on Week 28.

In addition to the above exploratory endpoints specified in the protocol, it has been decided to perform a retrospective collection of pre-study pulmonary function tests data and, depending on the completeness and usability of the obtained data, to provide descriptive analyses of pre-study evolution of PFT, and, if feasible, to conduct exploratory analyses on the relationship between this pre-study PFT data, and any change during the study and treatment effect.

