The time variations in historic FVC [% predicted] data (see section 8) will be modelled using a linear mixed effect model with random intercept and slope, with available historic FVC measurements for each patient (until baseline, baseline included) as dependent variable (outcome) and time (continuous variable calculated as the actual number of days before baseline) as explanatory variables (Statistical table 14.2.30.1.1 to 14.2.30.1.2, Figure 14.2.21.1.1 to 14.2.21.1.2). This analysis will be repeated using historic FVC [ml] measurement as dependent variable. (Statistical table 14.2.30.2.1 to 14.2.30.2.2, Figure 14.2.21.2.1 to 14.2.21.2.2). All available individual measurements will be provided in Listing 16.2.6.13.

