5.4 Data handling conventions

5.4.1 Baseline definitions

For both the efficacy and safety endpoints the last observation prior to the first dose of study treatment administration will be used as the baseline value. This will usually correspond to the measurement performed at day1 week 0 before first-dose. However, in case of missing value at day 1 week 0 the last available value recorded during screening will be used as baseline value.

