Vital Sign abnormalities	
 • Heart rate: <50 or >90 • Respiratory rate: <12 or >20 • Body temperature: $<36.5^\circ\text{C}$ or $>37.5^\circ\text{C}$ • Diastolic Blood Pressure: <60 or >90 • Systolic Blood Pressure: <90 or >140 • Oxygen Saturation: <90
Event Duration	$(\text{End Date}) - (\text{Start Date}) + 1$
Total Lung Volume in ml (TLV)	Total lung volume (excluding vessel volume) in ml
Normal Lung Volume in ml (NLV)	NLV=Areas of Normal lung in ml + Mild Low Attenuation Area (LAA) in ml
% of Normal Lung Volume	$100 * (\text{NLV in ml}) / (\text{TLV in ml})$
% of mild Low Attenuation Areas (LAA)	$100 * (\text{mild LAA in ml}) / (\text{TLV in ml})$
% of moderate Low Attenuation Areas (LAA)	$100 * (\text{moderate LAA in ml}) / (\text{TLV in ml})$
% of severe Low Attenuation Areas (LAA)	$100 * (\text{severe LAA in ml}) / (\text{TLV in ml})$
% Ground Glass (GG)	$100 * (\text{GG in ml}) / (\text{TLV in ml})$

% Honeycombing (HC)	$100 * (\text{HC in ml}) / (\text{TLV in ml})$
% Reticular Changes (RC)	$100 * (\text{RC in ml}) / (\text{TLV in ml})$
Interstitial Lung Abnormalities (ILA) in ml	$(\text{ILA in ml}) = (\text{GG in ml}) + (\text{RC in ml}) + (\text{HC I ml})$
% Interstitial Lung Abnormalities (ILA)	$\% \text{ILA} = \% \text{GG} + \% \text{RC} + \% \text{HC}$
Historic FVC (% predicted)	$(\text{Historic FVC \% predicted}) = [\text{Historic FVC (mL)} / \text{Reference Result of FVC (mL) at baseline}] * 100$

9 Tables, Figures and Listings

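### The exploratory pre-study FVC slope can be biased steep, by the entry rule for antifibrotic-treated patients and by a reference value fixed at baseline

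*SAP*

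**What the plan says.** - **Model.** SAP 5.2.5.3 (historic FVC) specifies a linear mixed model with random intercept and slope, "with available historic FVC measurements for each patient (until baseline, baseline included) as dependent variable (outcome"). Time before baseline is the only explanatory variable named. There is no stratum term, look-back window or minimum number of tests. The fit is also done in mL: "This analysis will be repeated using historic FVC [ml] measurement as dependent variable".
- **Entry rule.** Protocol 5.1.1, criterion 3, admits patients on pirfenidone or nintedanib only "without increase in FVC% predicted on two consecutive PFTs, including screening PFTs". Protocol 8.1 plans 75% of patients in this stratum.
- **Denominator.** SAP section 8 derives historic FVC % predicted by dividing each historic value by the "Reference Result of FVC (mL) at baseline".
- **On-study values.** SAP 4.1.1 takes FVC % predicted from the central vendor, "analysed without any transformation or derivation". The reference is set in a vendor specification that is not part of these documents.
- **Baseline.** SAP 5.4.1: "the last observation prior to the first dose of study treatment administration will be used as the baseline value". This is normally the Day 1 test, taken after the screening test used for selection.
- **Use.** SAP 4.1.3 foresees a descriptive analysis, depending on how complete and usable the data are and, if feasible, exploratory work "on the relationship between this pre-study PFT data, and any change during the study and treatment effect".

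**The concern.** Criterion 3 compares two noisy measurements and keeps the patient if the later one is not higher. Among those kept, the error of the earlier test is on average positive and that of the screening test negative. A slope fitted through both inherits a decline that is not in the lung. Later tests carry fresh errors, so the apparent decline eases after entry whatever the treatment.

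The fixed reference acts in the same direction. Predicted FVC falls with age in adults, so dividing an older measurement by the smaller baseline reference inflates it and steepens the line.

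The stake is one of interpretation. A pre-study slope shown beside on-study slopes invites a before-and-after reading, and under these rules some slowing could appear in the placebo arm as well as the PRM-151 arm. The SAP contains no safeguard against that reading.

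**Working it through.** **The plan's own figure.** The documents give no figure for the historic slope. The related design figure reproduces. The expected difference is 0.75 × (0.75 + 1.5) + 0.25 × (0.75 + 3) = 2.625. With SD 5, two-sided alpha 0.10, 80% power and 2:1 allocation, the placebo n is 1.5 × (1.645 + 0.842)² × 25 / 2.625² = 33.6, so 34, and 102 in total.

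**Inputs.**
- Mean decline on antifibrotics: −1.5 points per 28 weeks (Protocol 8.1), which is −1.5 × 52.18/28 = −2.8 points/year.
- Measurement SD: assumed 2.5. The text of Protocol 1.2 gives Day 57 change SDs of 3 and 3.8. Dividing by √2 gives at most about 2.1 to 2.7 per test.
- Between-patient slope SD: assumed 4 points/year. The SD of a 28-week change is then √(2 × 2.5² + (4 × 28/52.18)²) = 4.1, within the planned 5.
- Test times: assumed at −6, −1 (screening) and 0 months, with further tests at −12 and −18 months.

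**Step 1: effect of selection.** Let D be the screening test minus the previous test, g = 5/12 year apart.
- Mean of D = −2.8 × 5/12 = −1.167.
- Variance of D = (4 × 5/12)² + 2 × 2.5² = 15.28, so SD 3.909.
- Keeping D ≤ 0 gives z = 1.167/3.909 = 0.2985 and φ(z)/Φ(z) = 0.618, so D shifts by −3.909 × 0.618 = −2.416.
- True slope of those kept: −2.8 − (16 × 5/12)/15.28 × 2.416 = −3.85 points/year. This extra decline is real and would persist.
- Error shift: 6.25/15.28 × 2.416 = 0.988, upward on the previous test and downward at screening.

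**Step 2: excess in a least-squares slope.** Excess = −0.988 × g / Sxx, where Sxx is the sum of squared deviations of the test times in years.

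| Tests (months) | Sxx | Excess, points/year | Fitted slope |
|---|---|---|---|
| −6, −1, 0 | 0.1435 | −2.87 | −6.7 |
| −12, −6, −1, 0 | 0.6302 | −0.65 | −4.5 |
| −18, −12, −6, −1, 0 | 1.6056 | −0.26 | −4.1 |

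Simulation gives the same fitted values. Moving the prior test to 4 months before baseline in the three-test case gives −8.35 against a true −3.54.

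**Step 3: the planned mixed model.** This model gives short histories less weight, roughly 1/(16 + 6.25/Sxx). For three, four and five tests the weights are 0.0168, 0.0386 and 0.0503. With equal shares of each, the excess is (0.0168 × 2.87 + 0.0386 × 0.65 + 0.0503 × 0.26)/0.1057 = 0.82 points/year. That is 0.44 per 28 weeks in the stratum, and about 0.75 × 0.44 = 0.33 when pooled over strata.

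**Step 4: other settings.** A separate simulation set the slope SD so that the 28-week change has SD 5, with noise SD 2 to 3 and screening 4 weeks before baseline. The excess per 28 weeks was:
- one test, 13 weeks before screening: 1.8 to 3.3;
- one test, 26 weeks before screening: 0.7 to 1.6;
- two tests at 26-week gaps: 0.2 to 0.4;
- five tests at 26-week gaps: 0.02 to 0.05.

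In the stratum without the rule it was 0.

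**Step 5: reference effect.** Extra slope = 100 × (FVC as a fraction of predicted) × (annual fall in reference)/(reference). Assumed low end: 100 × 0.60 × 20/4000 = 0.30 points/year. Assumed high end: 100 × 0.75 × 30/3000 = 0.75 points/year. For FVC in mL it is 0.

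**The case against.** The strongest reply is that the SAP specifies no before-and-after comparison. The historic model uses pre-study data only, and SAP 4.1.3 makes any link to on-study change conditional on data quality and feasibility. That stands. A reader might infer that the SAP will report slowing in both arms, or that the treatment comparison is compromised. The documents support neither. Both rules act before randomisation and fall equally on the arms, so PRM-151 versus placebo is not biased.

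Other parts of the reply also stand:
- The largest excess needs every patient to have a single test before screening and a separate slope per patient. The planned mixed model and longer histories reduce it.
- The documents do not say whether the screening test counts as historic. If neither selected test enters the model, the entry-rule effect disappears.
- A single fixed reference is FVC in mL rescaled, a defensible choice for retrospective data. It distorts a contrast with on-study slopes only if the vendor's reference is updated for age, which cannot be seen here.
- The net direction is not established. Requiring FVC of at least 50% of predicted at entry can remove fast decliners and so act the other way.

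The mL repeat does not answer the entry-rule effect, because the selected errors are in the FVC measurement itself. Nor does the genuine selection of faster decliners, because the excess above is measured against the true slope of the same enrolled patients.

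**Conclusion.** The concern holds as a possibility that the SAP leaves open. The fitted historic slope can be steeper than the patients' true slope, and nothing in the model allows for it. In the antifibrotic stratum the excess is about 0.25 to 0.65 points/year with four or five tests, and about 3 with one test before screening. The number and spacing of tests drive this size, and neither is in the documents. The noise SD, slope SD and 6-month interval are assumptions. The reference effect adds about 0.3 to 0.75 points/year to the % predicted slope under the assumed reference fall.

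It would go too far to say that the slope is certainly too steep, or that false slowing will be seen. This is a minor point about an optional exploratory analysis. It leaves the primary comparison untouched and is worth settling because the remedy is nearly free.

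**What to change.** Amend SAP 5.2.5.3 and section 8 before unblinding:

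1. Fit and report the historic slope separately by randomisation stratum.
2. Compute historic % predicted with the reference for the patient's age at each test, using the same equation as the vendor's on-study values. Date of birth, sex, race and height are collected (Protocol 7.3 and 7.5). If the equations cannot be matched, rely on the mL analysis.
3. As a sensitivity analysis in the antifibrotic stratum, refit without the screening test and the test it was compared with, keeping Day 1. Report how many patients lose their slope.
4. State that any pre-study versus on-study change will be read only as a difference between arms.

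The cost is SAP wording and a little programming. Item 3 should stay a sensitivity analysis: patients with only one test before screening are left with Day 1 alone and no slope, and that is where the bias is largest.

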5.2.6 Safety analyses

Safety analysis will be based on the incidence, intensity, and type of adverse events, incidence of respiratory decline, Infusion related reactions, and clinically significant changes in the subject's physical examination, vital signs and clinical laboratory results. Safety variables will be tabulated and presented for all subjects who have received any amount of study medication.

5.2.6.1 Adverse events

Adverse event listings:

AE listings will be presented and sorted by treatment group, subject, primary system organ class, preferred term and verbatim text for all adverse events recorded during the study and will include duration of each episode.

The following listings will be produced:

- Listing of Adverse Events (Listing 16.2.7.1): All adverse events for each patient, including the same event on several occasions, giving both preferred term and the original term used by the investigator. The listing will be sorted by site and by treatment group and should include: Patient identifier / Age, race-ethnicity, sex, weight, height / The adverse event (preferred term, reported term) / Duration of the adverse event / Severity (mild, moderate, severe) / Seriousness (serious, non-serious) / Action taken with study drug (dose reduced, treatment interrupted-delayed, treatment permanently discontinued-omitted, none, not applicable) / Outcome (resolved, resolved with sequelae, ongoing, unknown) / Relationship to study drug (not related, possibly related, probably related) / Date of onset or date of clinic visit at which the event was discovered / Timing of onset of the adverse event.
- Listing of Deaths (Listing 16.2.7.2) and Serious Adverse Events containing the same information as above.

Adverse events tabulations:

Tabulation of adverse events will present for each cell the following information: number of patients with at least one occurrence of the event, corresponding percentage and number of events (if relevant). The following tables will be produced for the whole SAF population as well as by treatment group:

Summary of AE (Statistical Table 14.3.3):

- Any AE
- Any TEAE
- Any TEAE leading to permanent study treatment discontinuation
- Any TEAE leading to study discontinuation
- Any TEAE of severe intensity
- Any possibly or probably related TEAE
- Any SAE
- Any TESAE
- Any TESAE leading to study treatment permanent discontinuation
- Any TESAE leading to study discontinuation (optional)
- Any TESAE considered related to the study treatment
- Deaths (if any)
-

Detailed Tables on TEAEs:

- All TEAE by SOC and PT (Statistical Table 14.3.4.1)
- Most frequent TEAEs by SOC and PT and decreasing frequency (Statistical Table 14.3.4.2)
- All possibly or probably related TEAEs by SOC and PT (Statistical Table 14.3.4.3)
- All TEAE by SOC, PT and intensity (Statistical Table 14.3.4.4)

- All TEAE leading to permanent study drug discontinuation by SOC and PT (Statistical Table 14.3.4.5, only produced if more than 5 events)
- All TEAE leading to permanent study discontinuation by SOC and PT (Statistical Table 14.3.4.6, only produced if more than 5 events)

Detailed Tables on TESAEs:

- Any TESAЕ by SOC and PT (Statistical Table 14.3.5.1)
- All possibly or probably related TESAЕs by SOC and PT (Statistical Table 14.3.5.2, only produced if more than 5 events)
- All TESAЕ by SOC, PT and intensity (Statistical Table 14.3.5.3)
- All TESAЕ leading to permanent study drug discontinuation by SOC and PT (Statistical Table 14.3.5.4, only produced if more than 5 events)
- All TESAЕ leading to permanent study discontinuation by SOC and PT (Statistical Table 14.3.5.5, only produced if more than 5 events)
- Death: all causes of mortality and mortality due to respiratory declines (Statistical Table 14.3.5.6)

5.2.6.2 Respiratory decline events

Tabulation of respiratory decline events will present for each cell the following information: number of patients with at least one occurrence of the event, corresponding percentage and number of events. The following tables will be produced for the whole SAF population as well as by treatment group:

- All respiratory decline events by PT (Statistical tables 14.3.6.1)
- All respiratory decline events by PT and intensity (Statistical tables 14.3.6.2)
- All respiratory decline events by PT and seriousness (Statistical tables 14.3.6.3)

5.2.6.3 Infusion related reactions

Tabulation of infusion related reactions will present for each cell the following information: number of patients with at least one occurrence of the event, corresponding percentage and number of events. The following tables will be produced for the whole SAF population as well as by treatment group:

- All infusion related reactions by PT (Statistical tables 14.3.7.1.1)
- All infusion related reactions by PT and intensity (Statistical tables 14.3.7.1.2)
- All infusion related reactions by PT and seriousness (Statistical tables 14.3.7.1.3)

The potential influence of Anti-Pentraxin 2 antibodies (ADA) and occurrence of IRR will be studied by producing the same tables as described above breaking down the patients according to presence/absence of ADA (Statistical tables 14.3.7.2.1, 14.3.7.2.2 and 14.3.7.2.3).

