1.5. Risk/Benefit Assessment

PRM-151, a recombinant form of an endogenous human protein, has been well tolerated in preclinical toxicology studies and Phase 1 and 2 clinical studies, and has shown an early trend towards efficacy in subjects with IPF. Based on encouraging Phase 1 data in subjects with IPF, PRM-151 has the potential to be a safe, disease modifying treatment for a broad spectrum of fibrotic diseases, including IPF.

PRM-151 represents the recombinant version of an endogenous human serum protein, and as such was predicted to have a very favorable safety index. This prediction has been confirmed in multiple preclinical and clinical studies to date. Two Phase 1 studies of

PRM-151 administered IV to normal volunteers and IPF subjects have been completed, with no SAEs reported and no other safety signals seen. The single ascending dose study (PRM151A-11EU) tested dose levels as high as 20 mg/kg. The multiple ascending dose study (PRM151F-12GL) demonstrated that PRM-151 administered by 30-minute IV infusion on Days 1, 3, 5, 8 and 15 at up to 10 mg/kg was safe and well tolerated in subjects with IPF, with no SAEs noted in 57 days; similar types and number of TEAEs were reported in both PRM-151 and placebo treated subjects. Safety data from 27 subjects with MF, including 24 weeks of safety data in 20 subjects and an additional 12 weeks of safety data in 10, confirms the excellent safety profile of PRM-151 to date. Most adverse events have been Grade 1 or 2 and unrelated to PRM-151, and 5 possibly related SAEs, including one death, have been reported in a group of older subjects (median age 67 years) with a serious, life threatening disease.

Risks associated with PRM-151 are inherent in its being the recombinant form of a naturally occurring human protein, and consist of potential development of anti-drug antibodies and infusion reactions. PRM-151 has an endogenous counterpart, and, therefore, anti-drug antibodies could develop that could potentially affect the efficacy of PRM-151 treatments in addition to having the potential to cross-react with endogenous hPTX-2. Anti-drug antibodies were detected in 3 subjects in the MF trial, with no apparent impact on pharmacokinetics, safety, or efficacy. Two subjects had mild infusion reactions which were easily managed and prevented in the one subject that was rechallenged; anti-drug antibody was detected in one of them.

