5.2.4 Extent of exposure and compliance

Compliance with study treatment will be computed for each subject of the ATS and the PP populations as the proportion of the prescribed IMP that has been actually administered (see section 8). Treatment compliance will then be analyzed globally and by treatment group, as a numerical variable as well as a categorical variable (see section 8, Statistical table 14.1.32.1 to 14.1.32.2).

To analyse the extent of exposure the following variables will be summarised by treatment group for the SAF population (Statistical table 14.3.1):

- number of infusions received
- cumulative volume of IP actually infused
- duration (number of days) between first IP administration and last IP administration

The extent of exposure will also be assessed based on Pentraxin-2 levels. Descriptive statistics for raw values at each visit and for changes from baseline to each visit in Pentraxin-2 levels will be computed by treatment group. This analysis will be performed on both the ATS and the PP dataset (Statistical table 14.3.2.1 to 14.3.2.3, Figures 14.3.1.1 to 14.3.1.2). Individual measurements of Pentraxin-2 levels will be reported in Listing 16.2.6.7.

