Change in Patient Reported Outcomes will be assessed based on the King's Brief Interstitial Lung Disease Questionnaire (K-BILD) and Leicester Cough Questionnaire (LCQ). Descriptive statistics for raw values and change from Baseline to each visit in total score of both questionnaire will be computed by treatment group. Differences between treatment groups in change from baseline to week 28 for total score of each questionnaire will be tested using a similar approach to the one used for the primary analysis (see section 5.2.5.1). These analysis will be performed on both the ATS and the PP data sets (Statistical tables 14.2.20.1.1 to 14.2.20.3.2 and 14.2.21.1.1 to 14.2.21.3.2, Figures 14.2.17.1 to 14.2.17.2 and 14.2.18.1 to 14.2.18.2). All results of K-BILD and LCQ will be reported in Listings 16.2.6.4.1 to 14.2.6.4.2.2 and 16.2.6.5.1 to 16.2.6.5.2.2.

For the LCQ, in addition to the above approach, frequency of patients with changes below or above 1.3 (identified as the minimal important difference) will be tabulated by treatment groups at week 4, 8, 12, 16, 20, 24 and 28 (Statistical table 14.2.21.4.1 and 14.2.21.4.2).

Descriptive statistics for raw values at each visit and change from baseline to each visit in anti-Pentraxin-2 antibodies measurements will be computed by treatment group. This analysis will be performed on both the ATS and the PP dataset (Statistical 14.2.22.1.1 to 14.2.22.2.2). Individual measurements of anti-pentraxin-2 antibodies will be reported in Listing 16.2.6.8.

EO3: To assess the use of quantitative imaging in IPF

The correlation between baseline FVC [% predicted], DLCO (corrected for Hb, [% predicted]), TLC by nitrogen washout, PROs and 6MWD and total lung volume and volume of parenchymal features on HRCT (in ml and % of total lung volume) representative of ILA by quantitative imaging, as well as change from Baseline to Week 28 in FVC [% predicted], DLCO (corrected for Hb, [% predicted]), TLC by nitrogen washout, PROs and 6MWD and change from Baseline to Week 28 in total lung volume and volume of parenchymal features on HRCT (in ml and % of total lung volume) representative of ILA will be computed. This analysis will be performed on both the ATS and the PP dataset (Statistical tables 14.2.23.1.1 to 14.2.23.1.2).

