The relationship between Anti-Pentraxin 2 antibodies (ADA) presence and level of FVC [% predicted] in time will be studied by modelling the influence of presence/absence (and/or level) of ADA in the repeated measures mixed model used for the primary efficacy analysis (see section 5.2.5.1) and if relevant using non-parametric spline functions. The most parsimonious model will be chosen on the basis of the AIC (Statistical table 14.2.25.1 and 14.2.25.2).

Additional exploratory analysis: Baseline characteristics vs. FVC

If data lend themselves to it, additional exploratory analysis will be done to test for interaction between baseline characteristics (e.g., FVC/DLCO/6MWD) and change in FVC.

Exploratory analysis of PK/PD relationship

Descriptive statistics and correlation will be computed to explore the relationship of Pentraxin-2 levels vs FVC [% predicted]/FVC [ml]/slope of FVC ml at week 24 and 28, and the relationship of

Pentraxin-2 vs other PFTs/PROs/6MWT (Statistical table 14.2.26.1 and 14.2.26.2). If relevant the corresponding scatter plot will be produced.

Exploratory analysis of relationship between Pentraxin-2 levels and ADA

Correlation coefficient between Pentraxin-2 levels and ADA titer at week 28 will be computed (Statistical tables 14.2.27.1 and 14.2.27.2) and a scatterplot prepared (using logarithmic coordinates for titers).

Exploratory analysis of acute exacerbations

Tabulation of each type of acute exacerbations will be produced (Statistical table 14.2.28.1.1 and 14.2.28.1.2). Descriptive statistic and Kaplan-meier curve will be computed by treatment group for time to first reported acute exacerbation (Statistical tables 14.2.28.2.1 and 14.2.28.2.2).

Additional exploratory analysis: FVC [% predicted] separately on pirfenidone and nintedanib

The same model as the one for the primary analysis (see section 5.2.5.1) will be used separately on (i) patient on a stable dose pirfenidone and (ii) patient on a stable dose of nintedanib (Statistical table 14.2.20.1.1 to 14.2.20.2.2).

Additional exploratory analysis: time variation in historic FVC [% predicted; ml] measurements:

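### SAP 5.2.6.3 splits patients by ADA presence without tying ADA status to the time of each infusion, and ADA is related to pentraxin-2 only at Week 28, so a time-dependent link would be diluted

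*SAP*

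**What the plan says.** Protocol 1.5 states that the risks of PRM-151 "consist of potential development of anti-drug antibodies and infusion reactions", and adds that antibodies have the "potential to cross-react with endogenous hPTX-2".

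For infusion reactions, the SAP's only ADA analysis is in 5.2.6.3. The IRR tables (by preferred term, by intensity, by seriousness) are produced again, "breaking down the patients according to presence/absence of ADA" (Tables 14.3.7.2.1 to 14.3.7.2.3). Neither that section nor the derived-data list in SAP Section 8 says whether presence means at baseline, at any time, treatment-emergent, or before the reaction.

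For pentraxin-2, the only analysis that joins it to ADA is in SAP 5.2.5.3: "Correlation coefficient between Pentraxin-2 levels and ADA titer at week 28 will be computed", with a scatterplot. SAP 5.2.4 follows pentraxin-2 over time, but there "changes from baseline to each visit in Pentraxin-2 levels will be computed by treatment group", not by ADA status.

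The SAP also plans other looks at ADA. Section 5.2.5.3 has by-visit summaries ("Descriptive statistics for raw values at each visit and change from baseline to each visit in anti-Pentraxin-2 antibodies measurements will be computed", by treatment group) and an FVC analysis "modelling the influence of presence/absence (and/or level) of ADA in the repeated measures mixed model used for the primary efficacy analysis". Individual ADA values (Listing 16.2.6.8), pentraxin-2 values (Listing 16.2.6.7) and adverse events with onset date and timing (Listing 16.2.7.1) are all to be listed.

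Protocol Appendix A schedules pre-dose ADA and pentraxin-2 samples at baseline, at the Week 4 to 24 visits and at Week 28.

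**The concern.** ADA status changes during the trial, but a patient-level split gives each patient one label. Take a patient who reacts on Day 1 and turns ADA-positive at Week 12. Under an ever-positive label, that reaction counts as one with ADA, although no antibody had been detected when it occurred. More generally, a positive label sweeps in every infusion given before seroconversion, and the comparison drifts towards no difference. A patient who stops after a reaction has fewer later samples and so less chance of ever being labelled positive, which lowers the ratio further.

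For cross-reaction, the question is whether a patient's own pentraxin-2 falls once antibodies appear. A single Week 28 cross-section uses no baseline and misses ADA that has come and gone. It also loses most early stoppers, because SAP 5.4.4 moves their End of Study data to the visit after their last infusion. The by-visit pentraxin-2 summaries average any fall in a few patients over the whole arm.

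These are risks the protocol itself names, and all subjects may go on to open-label PRM-151 for an indefinite period (Protocol 4.1).

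**Working it through.** The documents give no figure for the ADA analyses. The one design figure used here is the 78 patients planned on PRM-151. Its source reproduces: 0.75 × 2.25 + 0.25 × 3.75 = 2.625, SD 5, two-sided alpha 0.10, power 80% and 2:1 allocation give 68 + 34 = 102 evaluable (power 80.4%). Enrolment is set at 117, of whom 78 receive PRM-151.

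**Assumed rates.** Protocol 1.5 reports ADA in 3 myelofibrosis subjects and infusion reactions in 2, and mentions 27 subjects with safety data. Taking 27 as the denominator is an assumption.
- ADA: 3/27 = 11.1% (exact 95% CI 2.4% to 29.2%). Of 78, that is about 9 (range 2 to 23).
- IRR: 2/27 = 7.4% per patient. Over 9 infusions, the risk per infusion is 1 − (1 − 2/27)^(1/9) = 0.85%.

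**Dilution with nobody stopping.** There are 9 infusions: Days 1, 3 and 5, then Weeks 4 to 24. Assume ADA onset is spread evenly over the seven visits from Week 4 to Week 28, an ever/never label, and an IRR risk multiplied by R only while ADA is present. For rare events the patient-level ratio is about 1 + (R − 1) × (share of infusions that are ADA-positive). If ADA persists, onset at Week 4, 8, …, 28 leaves 6, 5, 4, 3, 2, 1, 0 positive infusions, a mean of 21/7 = 3 of 9.

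| ADA lasts | Mean positive infusions of 9 | Formula, R = 3 | Simulated, R = 3 | Simulated, R = 5 |
|---|---|---|---|---|
| to Week 28 | 21/7 = 3.0 | 1 + 2 × 3/9 = 1.67 | 1.6 | 2.2 |
| 8 weeks | 11/7 = 1.57 | 1.35 | 1.4 | 1.7 |
| 4 weeks | 6/7 = 0.86 | 1.19 | 1.2 | 1.4 |

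From 67% (6/9) to 90% of the infusions in ever-positive patients are given while ADA-negative. Classifying each infusion by current status returns about 3 and about 5.

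**Early stopping.** A second simulation assumed 1% IRR per infusion, 1.7% new ADA per cycle and about 11% ever positive.

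| Share of IRR patients who stop | 0% | 50% | 100% |
|---|---|---|---|
| Ever/never label, true 3 | 1.62 | 1.36 | 1.09 |
| Ever/never label, true 1 | 1.01 | 0.73 | 0.47 |

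Classifying by the preceding sample returned 3.0 and 1.0 in every column.

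**At the trial's own size.** Under the second set of assumptions (true 3, no stopping), 78 patients yield about 27 ADA-positive infusions and 27 × 0.03 = 0.8 expected IRRs among them. That cell is empty in 47% of simulated trials, against 29% for the ever-positive patient cell. The exact 95% lower limit of the per-infusion ratio exceeds 1 in only about 9%.

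**Pentraxin-2 by arm.** If 11.1% of the arm lose all their pentraxin-2, the arm mean falls by 0.111 × 100% = 11%. If they lose half, it falls by 5.6%.

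**Residual drug.** Protocol 6.8 gives a half-life of 21 to 44 hours. Four weeks is 672 hours, or 672/44 = 15.3 to 672/21 = 32 half-lives. At most 2^(−15.3), about 0.003% of peak, remains. The four-weekly pre-dose levels are therefore essentially endogenous and suited to this purpose.

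**The case against.** The strongest case against is that this is a one-line definition gap in descriptive tables of a Phase 2 pilot. Listings of ADA, pentraxin-2 and event onset already exist, and with about nine positive patients the timing can be read case by case. The proposed table would often have an empty cell. The prior evidence is also mild: Protocol 1.2 reports no infusion reactions and no antibodies in the earlier IPF study, and Protocol 1.5 saw no apparent impact of ADA in myelofibrosis. Much of this stands. It limits what any table can show, and it makes the matter a cheap improvement. It does not justify leaving the classifier open, since any fixed label misplaces infusions given before seroconversion.

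Stronger readings a reader might infer are not supported:
- **That the SAP fixes an ever/never rule.** It leaves presence undefined in time. Ever/never is the assumption behind the ratios above.
- **That the planned tables would make antibodies look protective.** The ratios below 1 require patients to stop after an IRR. Protocol 6.2 and 7.12.1.2 provide for later infusions with premedication. With no stopping there is dilution and no false signal.
- **That the Week 28 correlation rests on about nine patients.** SAP 5.2.5.3 does not restrict it to ADA-positive patients. For r = −0.5 the 90% CI is −0.84 to 0.12 with 9 pairs, but −0.64 to −0.33 with 66 (78 × 0.85).
- **That ADA is otherwise unexamined.** The by-visit tables, listings and FVC model exist. None relates IRRs or pentraxin-2 to ADA over time.
- **That the protocol asserts ADA causes IRRs.** It lists the two side by side. The only link it reports is that one of two reacting subjects was ADA-positive.

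**Conclusion.** The point holds in a limited form. SAP 5.2.6.3 does not tie ADA status to the infusion, and the Week 28 correlation is the only analysis that joins ADA to pentraxin-2. With an ever/never label and no stopping, a true ratio of 3 would appear as about 1.6 if ADA persists, and as 1.4 or 1.2 if it lasts 8 or 4 weeks. Early stopping after an IRR would lower it further. These sizes rest on assumed ADA and IRR rates, onset and persistence, which the documents do not give. They describe bias in large samples, not what 78 patients would show. Classification by infusion removes that bias but does not overcome the small numbers.

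**What to change.** 1. In SAP 5.2.6.3, classify each infusion by the last ADA result before it. Days 3 and 5 use the Day 1 sample, and the Week 4 to 24 infusions use that visit's pre-dose sample. Within the PRM-151 arm, report IRRs per infusion and per subject by that status. Put the definition in Section 8.
2. In SAP 5.2.4, add the pentraxin-2 change-from-baseline table split by ADA status at each visit, including early-discontinuation samples. Use the four-weekly pre-dose samples, since a level drawn two days after a dose would still contain drug.
3. Keep the Week 28 correlation as supportive.
4. State that these tables are descriptive.

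The cost is SAP wording and a small set of tables. The samples are those in Protocol Appendix A, and Protocol 6.7 already requires infusion date and time in the eCRF, so each IRR can be matched to its infusion. (The short schedule in SAP 2.3.3, as it reads here, marks no Week 4 to 24 ADA sample, but it marks no pulmonary function test at those visits either, so Appendix A is taken as the guide.) The drawback is very small cells, often with zero IRRs.
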